# **10.2 Reporting of Adverse Events**

In addition, the following maternal events are examples of adverse events to be reported: Maternal or perinatal allergic reaction:

- Angioedema, anaphylaxis or generalized skin rash
- Transfer to Chronic Care facility (neonatal)

- Maternal arrhythmia (especially QT prolongation) or congestive cardiac failure (EF<45%)

- Neonatal arrhythmia (especially QT prolongation)
- Any adverse event leading to discontinuation of study medication or suspected to be due to the medication
- Maternal pulmonary thromboembolism
- Maternal admission to ICU
- Neonatal IVH Grade III or IV
- Prolonged maternal or term neonatal hospitalized

# 11. QUALITY CONTROL

Quality control and assurance are the responsibility of every member of the IDA trial.

All clinic personnel are responsible for understanding the protocol procedures.

Research Staff responsibilities:

- Maintaining the integrity of the protocol and regulatory document binder.
- Developing a data entry system that incorporates real-time data quality assurance features, such as range and logic checks
- Monitoring site initiation requirements.
- Monitoring the screening and randomization processes to ensure randomization of eligible participants and appropriate randomization allocation of participants.
- Generating timely web-based reports describing clinic and study performance, including but not limited to: a) recruitment b) visit adherence and visit completeness c) study intervention) data entry e) data completeness f) outcomes documentation
- Monitoring documentation of 100% of potential outcomes

#### 12. STATISTICAL ANALYSIS

#### 12.1 Statistical Considerations

Efficacy Endpoint(s): The primary outcome for this study is to assess the delta in hemoglobin pre and post intervention in both treatment groups. Our hypothesis is that the rate of increase of intravenous iron will be approximately 1.5g/dL higher in the IV iron cohort versus the oral iron cohort

Secondary Efficacy Endpoint(s): The secondary outcomes for this study include the following:

- correction of anemia at the time of birth hospitalization,
- rates of blood transfusion,

- neonatal outcomes such as APGARs and NICU admissions
- maternal/neonatal infection
- mode of delivery (NTSV)
- infant birth weight

# 12.2 Sample size determination

We estimated minimum sample size required for 90% power, one-sided  $\alpha$ =0.025, and estimated effect sizes for the outcomes of change in proportion of women (Hg <11g/dL) by birth hospitalization based on the findings of previous studies. Based on these parameters and allowing for 20% drop-out rate, the study requires 32 subjects per arm. The analysis plan and sample size calculation were developed in consultation with Maternal-Fetal Medicine Senior Biostatistician, [name] (Co-I). We plan to recruit up to 80 patients to account for potential loss to follow up. We plan to update this sample size calculation based on a pilot study that we are conducting at our institution. We also plan for a much larger sample size in order to conduct analyses stratified by race/ethnicity and to study rare secondary clinical outcomes, as well as possibly compare formulations of intravenous iron, none of which has been done previously.

# 12.3 Analyses

We will conduct an intent-to-treat analysis to compare the primary and secondary outcomes between the treatment arms. The primary outcome is the mean change in hemoglobin in oral vs IV iron over 4 weeks as well mean change in hemoglobin pre delivery. The primary outcome will be assessed using t-tests. Baseline characteristics between the groups will be compared using t-tests and chi-square tests. If there is an imbalance between the treatment arms, we will use multivariable regression modeling. Differences will be considered statistically significant at P<0.05.

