#### **Medications**:

Ferrous sulfate 325mg tablets every other day or 650mg (two 325mg tablets) po every other day per protocol

Ferumoxytol intravenous iron – 510mg x1 dose or 510mg x2 doses per protocol

Tylenol 650mg tablets (or 325mg tables x 2)

Analysis: Intent to Treat Outcome Measures: Primary composite:

- o Correction of anemia by time of birth
  - Change in hemoglobin
- o Rates of blood transfusion postpartum

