# Primary safety outcome:

- O Rates of adverse events
- o Compliance with medication
- o Severe neonatal composite morbidity
- o Severe maternal morbidity

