#### 3.2 Secondary Outcome

Evaluate the

- rate of patients who discontinued treatment,
- the rate of adverse events associated with treatment,
- the need for blood transfusion postpartum
- symptoms of patients before, during, and at the completion of therapy

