# Group 2: (oral iron)

- 8 weeks post-initiation labs to be timed with prenatal care where possible
- Pill count to occur with CTRU or MFM research staff to assess compliance
  - If compliance a concern, assess reasons why

[figure not shown]
In both groups, patient will complete a survey monitoring symptoms and adverse effects between 8-12 weeks after initiation of therapy.

Algorithm B: Eval for labs post 4 weeks treatment

\* Oral arm: if patients state they are intolerant to oral iron at any time during the study – refer to OB to discuss alternative treatment options

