# 7.3 Management of patient's intolerance to study intervention

#### Oral iron:

For adverse effects, particularly GI, consideration may be given for IV iron as this is standard of care. Per ACOG, intravenous iron is an approved indication for patient's intolerant of oral iron.

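### No adverse event analysis by iron received is planned, so an infusion reaction in an oral-arm woman moved to IV iron would be tabulated under oral iron

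*Combined protocol and SAP*

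**What the plan says.** Section 12.3 sets one analysis rule: "We will conduct an intent-to-treat analysis to compare the primary and secondary outcomes between the treatment arms". The synopsis also names intent to treat and no other set.

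Adverse events appear as an outcome in two places. Section 3.2 lists "the rate of adverse events associated with treatment" among the secondary outcomes, and the synopsis puts "Rates of adverse events" first under its primary safety outcome.

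Movement off oral iron is foreseen:

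- Section 7.3, oral iron: "For adverse effects, particularly GI, consideration may be given for IV iron as this is standard of care".
- Footnote to the week 4 algorithm, printed in section 7.2 and repeated for week 8: "if patients state they are intolerant to oral iron at any time during the study – refer to OB to discuss alternative treatment options".
- Section 7.8 expects that some women will not tolerate the tablets and will change to another treatment.

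The visit schedule in section 7 carries adverse event monitoring in both arms through 6 weeks postpartum. Section 9.2 allows event monitoring to continue for women no longer managed under the study algorithm.

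No section defines a treatment-received safety set, says how events after a switch are assigned, or asks for the replacement product and its start date.

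**The concern.** Intent to treat answers what follows from assigning a woman to one arm or the other. It does not answer which product an event followed. Once women can move from oral to IV iron, the two questions separate, and the outcome in section 3.2 is worded as the second.

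The hazard most affected is the one to which the protocol gives most attention: hypersensitivity to the infusion. It has a boxed warning in section 2.3.2 and a management algorithm in section 7.3. If the only planned table is by randomized arm, a reaction to IV iron in a woman who switched appears as an oral-arm event. The number of women exposed to IV iron is then reported nowhere. With 40 women per arm (section 4.3), a single misplaced event is visible in the results.

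**Working it through.** The plan states no figure on this point, so there is none to reproduce. The check has four steps.

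**1. Which set applies to adverse events.** Section 3.2 makes them a secondary outcome, and section 12.3 compares secondary outcomes by intent to treat. The secondary efficacy list in section 12.1 omits adverse events but offers no other set for them. The only stated rule is therefore comparison by randomized arm.

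**2. Whether a post-switch event is captured.** Sections 7.2, 7.3 and 7.8 foresee the switch. The visit schedule and section 9.2 keep monitoring in place. Such an event would enter the data and be counted in the oral arm.

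**3. Size, for infusion-related reactions only.**

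Inputs:
- Oral arm: 40 women (section 4.3).
- s, the share of the oral arm given IV iron: not in the documents; assumed 10%, 25% and 50%.
- p, the risk of any infusion-related reaction per infused woman: not in the documents; assumed 1%, 5% and 10%. Section 2.3.2 gives only the serious rate, below 1%.
- Such reactions are taken as absent on oral iron, and every IV-arm woman is taken as infused.

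Formulas:
- Arm difference by intent to treat: p − s·p = p(1 − s)
- Expected reactions counted under oral iron: 40·s·p
- Chance of at least one: 1 − (1 − p)^(40s)

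| s | Switchers | Women given any IV iron | Expected (chance of ≥1), p = 1% | p = 5% | p = 10% |
|---|---|---|---|---|---|
| 10% | 4 | 44 | 0.04 (4%) | 0.2 (19%) | 0.4 (34%) |
| 25% | 10 | 50 | 0.1 (10%) | 0.5 (40%) | 1.0 (65%) |
| 50% | 20 | 60 | 0.2 (18%) | 1.0 (64%) | 2.0 (88%) |

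At p = 5%, the difference of 5.0 points becomes 5 × 0.90 = 4.5, 5 × 0.75 = 3.75 or 5 × 0.50 = 2.5 points.

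For serious hypersensitivity, at a rate below 1%, 10 switchers give fewer than 10 × 0.01 = 0.1 expected events. The chance of even one is below 1 − 0.99^10 = 9.6%.

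**4. The overall adverse event rate.** The formula in step 3 does not carry over. Section 2.3.2 cites about 70% abdominal pain and 68% nausea on oral iron, so the oral background rate is far from zero. A woman considered for IV iron under section 7.3 has already had an adverse effect on oral iron. If events are counted per woman, a later infusion reaction adds nothing to the oral-arm rate. Stopping the tablets may also lower the number of later gastrointestinal reports in that arm. The net direction cannot be derived from the documents.

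**The case against.** **Intent to treat for safety is partly an inference.** Section 12.1 omits adverse events from its secondary list, and the synopsis gives them a separate safety heading. This stands as an ambiguity: the link runs through section 3.2. It does not remove the gap, because on the other reading adverse events have no stated analysis set at all.

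**Attribution is handled event by event.** Section 10.2 calls for reporting of "Any adverse event leading to discontinuation of study medication or suspected to be due to the medication", and under section 10.1 serious events go to the IRB while a DSMB monitors safety. A serious reaction in a switcher need not be misread when it is reported. That protects the individual report, but not the between-arm table.

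**The data are partly foreseen.** Section 8 lists a record of intervention discontinuation, section 7.8 tracks dispensing, and section 13 logs study infusions in the IV arm. None of these asks for the replacement product or its start date.

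**Intent to treat is a valid treatment-policy contrast.** This stands. It is a reason to keep the randomized-arm table and add to it, not to replace it.

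**Stronger readings that the documents do not support:**

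- A reader might infer that the plan makes IV iron look safer overall. That direction holds only for infusion-related reactions, for the reasons in step 4.
- A reader might pool switchers with the IV arm, so that one reaction among 10 switchers becomes 1/50 for IV iron rather than 0/40 in the IV arm and 1/40 in the oral arm. With no events, the one-sided 95% upper bound would be 1 − 0.05^(1/50) = 5.8% rather than 1 − 0.05^(1/40) = 7.2%. As statements about ferumoxytol, these need every switcher to receive ferumoxytol. Sections 7.2 and 7.3 mention only alternatives or IV iron and name no product.
- A reader might take the cited discontinuation of oral iron in about half of patients (section 2.2) as the switch rate. Discontinuation is not a switch to IV iron, section 7.3 says only that IV iron may be considered, and section 4.2 cites fewer side effects with intermittent dosing (RR 0.41).

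**Conclusion.** The point holds as a gap in the safety analysis. The only stated comparison is by randomized arm, one-way movement to IV iron is foreseen, and nothing assigns events after a switch. An infusion-related reaction in a switcher would be tabulated under oral iron.

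For that class of event, the arm difference shrinks by the factor (1 − s), a loss of 10% to 50% over the assumed range. This rests on an assumed switch share, no such reactions on oral iron, and a fully infused IV arm. The practical effect falls mainly on milder reactions, since few serious ones are expected among switchers. No direction is claimed for the overall adverse event rate.

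The change is worth making because it is cheap, and because product and date may be hard to recover later if they are not recorded. The point concerns analysis and data capture only. It takes no position on the clinical switching rule.

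**What to change.** In section 12.3:

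- Keep intent to treat for the efficacy outcomes, and keep the adverse event table by randomized arm.
- Add a table of adverse and serious adverse events by iron received at onset: oral only, ferumoxytol, or non-study IV iron. Give the number of women exposed in each category.
- State that events after a switch are assigned to the new product.
- Label the treatment-received table as a non-randomized comparison.

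In REDCap, record the date of any switch and the product given.

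The cost is a few sentences in the plan, one more table and two data fields. The downside is that women who switch are a selected group, so the added table supports attribution and exposure counts, not a causal comparison of the two treatments.

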# 3. OBJECTIVES

# 3.1 Primary Outcome

**Perform a pilot randomized control trial of oral ferrous sulfate to IV ferumoxytol in women with IDA in the second and third trimester of pregnancy.** We will *test the hypotheses* that 1) intravenous (IV) iron therapy will increase hemoglobin more with IV iron than oral iron over a 4 week period, approximately 0.8 g/dL in the IV group and 0.5g/dL in the oral arm  and 2) IV iron will improve anemia at the time of birth admission, 1.5 g/dL for IV iron and 1 g/dL for oral iron supplementation, the standard of care

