# 5.9 Frequency of Labs

The timing of follow up labs is determined by the expected amount of time a participant should see an increase in hemoglobin. The hypothesis is that 1) intravenous (IV) iron therapy will increase hemoglobin more with IV iron than oral iron over a 4 week period, approximately 0.8 g/dL in the IV group and 0.5g/dL in the oral arm and 2) IV iron will improve anemia at the time of birth admission, 1.5 g/dL for IV iron and 1 g/dL for oral iron supplementation, the standard of careThe estimates are informed from a 2018 study which reflected a 1.5 g/dL increase in hemoglobin by time of delivery in the intravenous group.

The follow up and reassessment is further informed by Micheal Auerbach's et al approach to treatment of IDA in pregnancy.

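### Section 12.3 tests two primary hemoglobin changes at P<0.05 without a success rule, the stated 90% power belongs to a different endpoint, and the assumed treatment effect differs between sections

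*Combined protocol and SAP*

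**What the plan says.** **Primary outcome.** Section 12.3 makes the primary outcome the mean hemoglobin change "over 4 weeks as well mean change in hemoglobin pre delivery". It specifies t-tests and adds "Differences will be considered statistically significant at P<0.05". Sidedness is not stated. The synopsis objective and section 3.1 number the two aims or hypotheses 1) and 2), but neither calls this a testing order.

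Other sections name the primary differently:
- The synopsis outcome list gives a primary composite of anemia correction by birth (with hemoglobin change beneath it) and postpartum transfusion.
- Section 12.1 gives one hemoglobin change without a time point. It lists "correction of anemia at the time of birth hospitalization" and transfusion as secondary.
- Section 3.2 also lists transfusion as secondary.

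**Sizing.** Sections 4.4 and 12.2 give 90% power at one-sided 0.025, with 32 per arm after allowing for 20% drop-out. The endpoint is the change in the proportion of women with hemoglobin below 11 g/dL by birth hospitalization. Recruitment is 80, 40 per arm (section 4.3).

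**Effect.** Section 12.1 expects the rise to be "approximately 1.5g/dL higher in the IV iron cohort versus the oral iron cohort". Sections 3.1 and 5.9 expect "approximately 0.8 g/dL in the IV group and 0.5g/dL in the oral arm" over 4 weeks and "1.5 g/dL for IV iron and 1 g/dL for oral iron supplementation" at birth admission. Section 5.9 adds that the source study "reflected a 1.5 g/dL increase in hemoglobin by time of delivery in the intravenous group".

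**The concern.** With two primary tests and no success rule, a reader cannot tell what result would make the trial positive. If one significant result is enough, the error rate is not the nominal 5%. If both are needed, the error is controlled, but the chance of success is bounded by the weaker comparison, and the plan gives power for neither.

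The stated 90% power does not fill that gap, because it belongs to a proportion that section 12.3 does not name as primary and that section 12.1, as correction of anemia, lists as secondary. Nor can a reader work out the power, because the stated between-arm difference ranges from 0.3 to 1.5 g/dL, a factor of five, and no SD is given. The trial is open label and has several candidate primaries on record, so the choice should be fixed before results by arm are seen.

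**Working it through.** **1. The plan's own figure.** The 32 per arm cannot be reproduced, because the two proportions are not stated. Illustrative pairs reach it: 0.90 against 0.45 with continuity correction needs 25 per arm, and 25/0.8 = 31.25, rounded up to 32; 0.90 against 0.50 without correction needs 26, and 26 × 1.2 = 31.2, rounded up to 32. Neither pair is in the documents.

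**2. False positive chance if either test suffices.** Inputs: two tests, each at two-sided 0.05 (section 12.3; two-sided is inferred from the one-sided 0.025 in sections 4.4 and 12.2), and no true difference. The correlation r between the two changes is not given, so a range is shown. Formula: 1 − P(|Z1| < 1.96 and |Z2| < 1.96), bivariate normal.

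| r | Either suffices |
|---|---|
| 0 | 9.75% (1 − 0.95²) |
| 0.5 | 9.1% |
| 0.7 | 8.3% |
| 0.9 | 7.0% |
| 0.95 | 6.5% |
| 0.99 | 5.7% |

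Simulated t-tests at 32 per arm agree (9.1% at 0.5, 7.1% at 0.9). A positive r is likely because both changes subtract the same baseline. With equal variances, r = (1 + rf − 2rb)/(2 − 2rb), where rb is each follow-up's correlation with baseline and rf is the correlation between follow-ups; this equals 0.5 when rf = rb. If P<0.05 meant one-sided, the figures would be 8.8% at r = 0.5 and 6.3% at 0.95.

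**3. False positive chance if both are required.** If neither effect is real, it is 10% minus the figure above: 0.9% at r = 0.5 and 3.5% at 0.95. If exactly one effect is real, it is at most 5%.

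**4. Differences implied by the text.**
- 4 weeks: 0.8 − 0.5 = 0.3 g/dL (sections 3.1 and 5.9).
- Birth admission: 1.5 − 1.0 = 0.5 g/dL (sections 3.1 and 5.9).
- Section 12.1: 1.5 g/dL between arms.

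**5. Power of one t-test.** Noncentral t, two-sided 0.05, 2n − 2 degrees of freedom, noncentrality (difference/SD) × √(n/2). For example, with 0.3 g/dL, SD 0.9 and n = 32, noncentrality is (0.3/0.9) × 4 = 1.33 and power is 26%. The SDs of 0.7, 0.9 and 1.1 g/dL are assumptions. Two evaluable sizes are shown: 40 × 0.8 = 32 from planned recruitment, and 32 × 0.8 = 25.6, about 26, because the plan's 32 already allows for drop-out.

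| Difference | Evaluable per arm | SD 0.7 | SD 0.9 | SD 1.1 |
|---|---|---|---|---|
| 0.3 | 32 | 39% | 26% | 19% |
| 0.3 | 26 | 33% | 22% | 16% |
| 0.5 | 32 | 80% | 59% | 43% |
| 0.5 | 26 | 71% | 50% | 36% |
| 1.5 | 32 | >99% | >99% | >99% |

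At 32 per arm, 90% power needs an SD no larger than 0.36 for 0.3 g/dL, 0.61 for 0.5 and 1.82 for 1.5. The chance that both the 0.3 and 0.5 comparisons are significant, simulated over r = 0.5 to 0.95, is about 37–39%, 22–26% and 13–19% at the three SDs.

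**The case against.** **The inflation depends on a reading that the plan does not adopt.** This stands. The documents do not say that either test suffices, so a reader who infers that the trial's error rate is 9% goes too far. The supported statement is that no rule exists and that one natural rule would exceed 5%. Nor is 6.5% a floor. Enrollment can run to 34 weeks 6 days (section 5.4), so a late 4-week draw can fall close to the birth-admission draw, which would push the correlation up and the excess down.

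**The aims are numbered 1) and 2).** The numbering could be meant as an order, but no section says that the second is tested only if the first succeeds.

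**The trial is a pilot.** Section 3.1 says "Perform a pilot randomized control trial of oral ferrous sulfate to IV ferumoxytol in women with IDA", and section 12.2 plans to update the size from a pilot at the institution. Whether that pilot is this trial is unclear. This limits the consequence of low power. It does not remove the point, because the plan still sets a significance rule and cites 90% power.

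**The SDs are assumed.** They are, so a reader might infer that the trial is underpowered, and the documents do not settle that. They show only that the answer turns on which stated difference is meant.

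**Section 12.1 is merely less specific than 12.3 about timing.** Agreed. On the primary, the conflict lies with the synopsis composite and the sizing endpoint.

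**Conclusion.** The point holds and should be corrected, although the pilot status limits the damage. Three things are established from the text alone: two primary tests lack a success rule; the 90% power refers to neither of them; and the 1.5 g/dL difference in section 12.1 is incompatible with the 0.3 and 0.5 g/dL implied by sections 3.1 and 5.9. The synopsis composite, which includes transfusion, also conflicts with sections 3.2, 12.1 and 12.3.

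The sizes are conditional. The excess over 5% arises only if either test suffices. Its limit of 9.75% assumes two-sided tests and non-negative correlation. The power figures rest on assumed SDs.

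Section 5.9 uses 1.5 g/dL for the rise within the IV arm. A reader might infer that section 12.1 restates that rise as a between-arm difference by mistake. The coincidence makes this plausible, but the documents do not confirm it, and only the sponsor can say.

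**What to change.** Before outcomes are compared by arm:

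1. In section 12.3, either name one primary hemoglobin comparison and test the other after it in a fixed sequence, each at two-sided 0.05, or keep both as co-primary under the Hochberg procedure at 0.05. State that tests are two-sided. Say that the pre-delivery value is the birth-admission value, if that is intended.
2. In sections 4.4 and 12.2, state that the 90% power is for the proportion with hemoglobin below 11 g/dL and not for the hemoglobin changes, and give power for the chosen primary with its SD and source. Alternatively, make correction of anemia at birth admission the primary, with a test for proportions and the two assumed proportions stated.
3. Reconcile the 1.5 g/dL in section 12.1 with the 0.3 and 0.5 g/dL in sections 3.1 and 5.9, saying whether it is a within-arm rise or a between-arm difference.
4. Make the synopsis objective, the synopsis outcome list and sections 3.1, 3.2, 12.1 and 12.3 name the same primary. Which one, and whether the composite stays, is the sponsor's choice.

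**Cost.** No new patient data are needed, but the SD or the proportions must be sourced. Under a fixed sequence the second claim depends on the first. With the 4-week change first, the assumed SDs and 32 evaluable per arm, the birth-admission claim would be blocked in about 61% to 81% of trials (100% minus the 39% to 19% power for 0.3 g/dL). Hochberg avoids that dependence and held the simulated error at 4.1% to 5.0% for correlations from 0.95 to 0. It costs some power, because when one comparison fails the other must reach two-sided 0.025. Making correction of anemia the primary keeps the existing sizing basis but dichotomizes hemoglobin, which loses information.

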# 5.4 Screening/Re-screening

Patients may be included in the study up to 34 weeks 6/7 days. If the above inclusion criteria are met and exclusion criteria are absent, patients should be approached for study participation (if not already done) and randomization. All women who have a diagnosis of IDA should have the screening form initiated. The screening number will be generated electronically with REDCap is accessed and participant information is entered.

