#### After randomization:

- Provide medication and instructions based on the treatment arm randomized to
- Provide the group algorithm to both patient and provider.

Once the participant is randomized, the treatment algorithms will be conspicuously placed in the patient's medical record (whether electronic or paper medical record is utilized) such that providers will be aware of treatment plan at all times.

In both groups, serial CBC follow up and survey for symptoms will be assessed. Baseline data consisting gestational age of pregnancy, body mass index, pre-pregnancy weight and other prenatal data including baseline BP at the randomization visit will be included. Patients will be assigned to treatment groups by a concealed randomization allocation sequence using REDCap.

The categories of patients randomized:

Patients consenting to the study will be randomized 1:1 to two treatment groups

Group 1: Patients randomized to the IV iron group will receive treatment as follows:

- Women with Hgb 9-10.9 g/dL will receive one dose of 510 mg IV ferumoxytol
- Women with Hg 7-8.9 d/dL will receive two doses of ferumoxytol 510 mg 3-8 days apart for a maximum of dose of 1020 mg (see **Figure 2**).
- Patients will receive 650mg of Tylenol prior to initiation of the infusion
- The ferumoxytol is administered as an infusion for approximately 15-30 minutes. Patients will receive the IV iron at Stanford's Clinical and Translational Research Unit (CTRU) outpatient clinics with vitals collected before infusion and monitoring for 30minutes after infusion. Alternatively, patients who are admitted to the antepartum unit may receive the infusion inpatient.

For the IV iron group, follow up labs will be performed at 4 and 8 weeks after completion of infusion/s;

Group 2: The standard of care oral iron group will be prescribed 1-2 ferrous sulfate 325 mg tablets to be taken by mouth **every other day** until delivery. Dosage will be as follows for standardization:

- one ferrous sulfate tablet every other day if Hg 9-10.9 g/dL, and
- two tablets once every other day if Hg 7-8.9 g/dL.
- Oral medications will be dispensed by the CTRU or by the Outpatient Investigational Pharmacy (final confirmation pending contracts)
- Follow up labs will be drawn for both groups. For the oral iron group, it will be drawn 4- and 8-weeks post initiation of treatment

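### Section 12.3 tests both primary hemoglobin changes with unadjusted t-tests and adjusts only if imbalance is seen; a prespecified ANCOVA on baseline hemoglobin would be at least as precise and would fix the model in advance.

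*Combined protocol and SAP*

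**What the plan says.** Section 12.3 of the combined protocol and SAP names two primary contrasts: "The primary outcome is the mean change in hemoglobin in oral vs IV iron over 4 weeks as well mean change in hemoglobin pre delivery". For the method it states "The primary outcome will be assessed using t-tests". Covariates enter only conditionally: "If there is an imbalance between the treatment arms, we will use multivariable regression modeling". The section does not say what counts as an imbalance or which covariates would be used. The level is "Differences will be considered statistically significant at P<0.05". The population is given as "We will conduct an intent-to-treat analysis to compare the primary and secondary outcomes between the treatment arms", and no method for missing values is stated.

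Three other places bear on the point.

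- **Entry.** Section 5.4 states "Patients may be included in the study up to 34 weeks 6/7 days". Section 1.1.2 gives 24 to 28 weeks as the preferred window for the entry labs.
- **Clock.** In the IV arm, "follow up labs will be performed at 4 and 8 weeks after completion of infusion/s" (Section 6, After randomization). In the oral arm the same draws are counted from the start of treatment.
- **Delivery value.** The admission blood count is routine at the delivering hospital and is taken from the chart (Sections 7.7 and 7.9.1).

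**The concern.** A t-test on change gives baseline hemoglobin a fixed coefficient of one. Unless follow-up hemoglobin moves one-for-one with baseline, that adds noise which a regression on baseline would remove. With at most 80 women and planned differences of 0.3 g/dL at 4 weeks and 0.5 g/dL at birth admission (Section 3.1), avoidable noise matters.

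The conditional adjustment is a second weakness. Under randomization any imbalance is due to chance, and how large it is says nothing about how strongly the covariate predicts the outcome. With neither trigger nor covariates defined, whether the reported estimate is adjusted is decided after the data are seen. The same trial could report either of two estimates.

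The visit schedule adds a smaller issue. Some women who enter late will have delivered before the 4-week draw is due, and the plan does not say how they are handled.

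**Working it through.** **The plan's own figure.** Section 12.2 says "We estimated minimum sample size required for 90% power" and reaches 32 per arm. It sizes on a proportion (hemoglobin below 11 g/dL at birth) and does not state the two proportions. After 20% loss, 32 × 0.8 = 25.6 evaluable per arm, which fits many pairs, for example 0.50 vs 0.10 or 0.90 vs 0.50. The figure cannot be reproduced. It also gives no hemoglobin SD or correlation, so the values below are assumptions shown as ranges.

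**Formula.** Let s0 and s1 be the baseline and follow-up SDs, k = s0/s1, and r their within-arm correlation. Per woman:

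- change score variance = s0² + s1² − 2·r·s0·s1
- ANCOVA residual variance = s1²·(1 − r²)
- ratio = (k² + 1 − 2rk)/(1 − r²) = 1 + (k − r)²/(1 − r²)

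The added term is a square, so in large samples ANCOVA is never less precise. With equal SDs the ratio is 2/(1 + r).

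**Results** (s1 = 0.9 g/dL; variance cut = 1 − 1/ratio):

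| s0 | r = 0.4 | r = 0.6 | Variance cut |
|---|---|---|---|
| 0.9 | 0.36/0.84 → 1.43 | 0.16/0.64 → 1.25 | 20%–30% |
| 0.75 | 0.188/0.84 → 1.22 | 0.054/0.64 → 1.09 | 8%–18% |
| 0.6 | 0.071/0.84 → 1.08 | 0.004/0.64 → 1.01 | 1%–8% |

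(Cells show (k − r)²/(1 − r²), then the ratio.) The lower rows matter because eligibility restricts baseline to 7–10.9 g/dL while follow-up is unrestricted. Modelling the truncation directly, with baseline SD 0.44–0.71 and the regression slope held at 0.4–0.6, gives ratios of 1.06–1.27, a cut of about 6%–21%.

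**In g/dL**, at 40 per arm and r = 0.5, the 95% half-width is 1.96 × SD × √(2/40):

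- ANCOVA: SD 0.9 × √0.75 = 0.779, half-width 0.34.
- t-test, s0 = 0.9: SD 0.90, half-width 0.39.
- t-test, s0 = 0.6: SD √(0.36 + 0.81 − 0.54) = 0.794, half-width 0.35.

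Estimating the slope costs about 1/(80 − 4) = 1.3% in variance, which cancels the gain at the weakest corner of the table but nowhere else.

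**Late entry.** For entry at 34w6d, the 4-week draw falls at 38w6d in the oral arm. With two infusions 8 days apart it falls at 34w6d + 8 days + 4 weeks = 40w0d, before any wait for the first infusion. Assuming delivery at mean 39 weeks (SD 1.5–2.0) and a 1-week wait for infusion, the share missing the draw is:

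| Entry | Oral | One IV dose | Two IV doses |
|---|---|---|---|
| Uniform, 24 to 34w6d | 5%–7% | 10%–12% | 19%–20% |
| 24–28 weeks only | about 0% | about 0% | about 0% |

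In simulation with SD 0.9, correlation 0.4–0.6 and uniform entry, the resulting bias was about 0.01 g/dL.

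**What repeated measures add.** Expected-information variances were compared over correlations of 0.3–0.8 with 0–30% of 4-week values missing. A baseline-constrained mixed model gave 0–5.5% lower variance than complete-case ANCOVA at 4 weeks. A mixed model on change scores without baseline gained nothing with full data and about 7% over the t-test at 30% missing. The gain comes mainly from baseline.

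**The case against.** The strongest defence is that a t-test on change is a valid comparison of randomized arms in a trial that Section 3.1 calls a pilot, that regression is already in the plan, and that the gain could be a few percent if the baseline SD is small. All of this stands. It limits the size of the point but does not remove it, because adjustment costs almost nothing and the trigger for the existing regression is undefined.

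A reader might infer something stronger: that the t-tests drop women who deliver early, that this contradicts the intent-to-treat label, and that one mixed model is needed to recover them. The documents do not support that.

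- A woman who delivers before her 4-week draw leaves the 4-week test only. Her routine admission value keeps her in the pre-delivery contrast, which is itself primary. Only the 8-week value has no stated role in Section 12.3.
- Complete-case analysis is inferred from silence on missing data; the plan does not state it.
- Material loss requires much late entry, whereas screening rests on the routine 24 to 28 week blood count (Section 5.1). Sections 7.7 and 7.9.1 give 30 and 32 weeks as outer limits for the randomization labs.
- The mixed model has costs of its own. It assumes missing at random and targets a hypothetical 4-week value in women already delivered. Treating delivery as a single visit would also ignore that it can fall under 4 or over 12 weeks after treatment.

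**Conclusion.** The point holds as a nearly free improvement to a valid analysis. Unadjusted t-tests with adjustment only on observed imbalance give up precision and leave the primary model open to the data. The variance cut is about 20%–30% with equal SDs and about 1%–18% if the baseline SD is 0.6–0.75 against 0.9. Both ranges rest on assumed correlations of 0.4–0.6, since the documents give neither SDs nor correlations. A claim that adjustment is always worth a quarter or more extra patients would use only the equal-SD case.

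Missed 4-week draws are likely for some late entrants, probably more in the IV arm because its clock starts after the last infusion. They affect one of the two contrasts, and the bias appears small. They do not show that the trial's result would be wrong. Which contrast is primary, and how the 0.05 level is shared between them, is a separate question that baseline adjustment does not settle.

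**What to change.** In Section 12.3, replace the t-tests and the conditional regression as follows.

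1. For each primary contrast (4 weeks and delivery admission), fit an ANCOVA of follow-up hemoglobin on arm and baseline hemoglobin, in all randomized women with a value, analysed as randomized and whatever the observed balance. Using change as the response gives the same arm difference.
2. Report the adjusted difference with its 95% CI, and keep the unadjusted t-test as a sensitivity analysis.
3. State that women who deliver before the 4-week draw have no 4-week value, report their number by arm, and keep them in the delivery contrast.
4. Optionally, add a baseline-constrained mixed model as a sensitivity analysis. State its missing-at-random assumption and the hypothetical 4-week value it targets, and let it allow for the variable timing of delivery.

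The cost is a few sentences of SAP text, settled before outcome data are examined by arm, and slightly more analysis work. No new visits, samples or patients are needed.
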